## 3 ELIGIBILITY CRITERIA

### 3.1 Inclusion Criteria

#### Definitions:

- **Androgen Deprivation Therapy** includes LHRH agonist or LHRH antagonist or bilateral orchiectomy. Anti-androgen receptor blockers (e.g. bicalutamide) do not constitute androgen deprivation therapy.
- **Protocol specified therapy** refers to the androgen deprivation therapy (see above) with or without radium-223 dichloride.

1. All subjects or their legally authorized representative must be informed of the investigational nature of the study and provide written informed consent and HIPAA authorization for release of personal health information before performance of any study related procedure not part of routine medical care.  
**NOTE:** HIPAA authorization may be included in the informed consent or obtained separately.
2. Men  $\geq$  18 years of age at the time of informed consent.
3. Histological or cytological evidence of prostate adenocarcinoma.
4. All subjects must have radiologic or pathologic evidence of skeletal metastases with  $\geq$  2 skeletal lesions with or without pain at baseline on bone scan or axial imaging or with 1 skeletal lesion and bone pain within 28 days prior to the registration.
5. All subjects must have a radiographic assessment (chest or abdominal/pelvic CT or MRI) within 28 days prior to registration but do not need to have measurable disease.
6. ECOG (Eastern Cooperative Oncology Group) Performance Status of 0-2 within 28 days prior to registration (see Study Procedures Manual [SPM] for ECOG Performance Status definitions). ECOG Performance Status of 3 will only be allowed if judged by the site investigator as attributable exclusively to bone pain.
7. Subjects must fall into one of the two populations below:
  - **Early Induction Group:** Subjects who have started androgen deprivation therapy (luteinizing hormone–releasing hormone (LHRH) agonist or antagonist therapy with or without an antiandrogen agent) a maximum of 28 days before registration and who otherwise meet all the eligibility criteria.
  - **Late Induction Group:** Subjects who have NOT started any androgen deprivation therapy (luteinizing hormone–releasing hormone (LHRH) agonist or antagonist therapy with or without an antiandrogen agent).

8. Anti-androgen receptor antagonist therapy must be bicalutamide. Subjects already started on other anti-androgens must be willing to switch over to bicalutamide.

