Some subjects may be confused by the response choices. They may want to respond with “I don't know” or some other response choice that is not available. If this happens, try to help the subject choose one of the response categories by saying something like: “I know that it may be difficult for you to choose an answer, but which of these answers do you think comes closest to the way that you are thinking or feeling?” If the subject still cannot select an answer, accept the questionnaire as is. Occasionally, subjects may not report having difficulty with a question or the

response choices, but still may hesitate or refuse to answer an item or items. If this happens, accept the questionnaire as is. If a subject asks for interpretation of his responses or asks for his scores on the questionnaire, tell him that you are not trained to score or interpret the questionnaire. Emphasize that their answers will be kept confidential.

Completed questionnaire: Thank the subject once he has completed the questionnaires and you have checked them for completeness.

B. WHO Ladder scale:

WHO Score	Description	Opioid Use
0	No pain	
1	Mild pain	using non-opioid +/- adjuvant daily on average
2	Moderate pain	using weak opioid +/- non-opioid +/- adjuvant daily on average. Weak opioids include codeine phosphate, dextropropoxyphene, dihydrocodeine or tramadol.
3	Severe pain	Strong opioid +/- non-opioid +/- adjuvant daily on average. Strong opioids include morphine, oxycodone, fentanyl, buprenorphine, oxymorphone, hydromorphone.

The WHO ladder score will be assigned by the treating physician based on the subject’s daily analgesic use on average. Score will be assigned pre-treatment on Cycle 1 Day 1 of (Late Induction group) or Cycle 2 Day 1 (Early Induction group), Cycle 4 Day 1 and at end of study visit. At each time-point, a single numeric score (0, 1, 2 or 3) will be assigned based on the scale as above.

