## **12. STATISTICAL CONSIDERATIONS**

### **12.1 Study Design**

Newly diagnosed metastatic prostate cancer subjects with  $\geq 2$  bone metastases will be accrued and randomized 1:2 to ADT without or with Radium-223 dichloride respectively. The primary aim of the study is to determine if the addition of Radium-223 dichloride to ADT will improve efficacy in this prostate cancer population. The primary efficacy endpoint is radiographic progression-free survival (rPFS). We expect the control arm with ADT alone to have a 12 month median rPFS. The addition of radium-223 to ADT will target an improvement of 7 months for a median rPFS of 19 months. A total of 140 events are required for at least 90% power to detect Hazard Ratio of 0.632 with a one-sided alpha of 0.1. The study powering is based on assumptions of 19 months median rPFS in the experimental arm and 12 months median rPFS in the control arm. Assuming exponential time to event data, a yearly dropout rate of 10% with

accrual in 24 months and study duration of 48 months, 204 subjects will provide 90% power with a 10% one-sided type I error. Hypothesis testing for the primary endpoint will be conducted at a one-sided 0.10 significance level using a stratified log-rank test. Randomization of 68 subjects to the ADT arm and 136 subjects to the ADT+R arm will be completed with stratification by extent of disease (<6 skeletal metastases without visceral disease versus  $\geq 6$  skeletal metastases or visceral disease) and baseline alkaline phosphatase (normal versus abnormal), abnormal alkaline phosphatase defined as  $> 130$  IU/L. If time anticipated for the number of events required for analysis significantly exceeds 48 months, the sponsor may enroll additional subjects to reach required number of events.

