We will evaluate the distribution of pre-randomization marker levels (ALP and bone markers) among those who have and have not started ADT prior to randomization. If it appears that the prior initiation of ADT impacts the study entry bone marker levels to a fair extent, then all marker analyses will be conducted stratified by ADT initiation status. Descriptive statistics by arm will report the time to ALP progression among all subjects using Kaplan-Meier methods. ALP and serum bone markers will be reported by arm for each time-point using means or medians and corresponding measures of variability for all subjects with serum. Percentage change in ALP from baseline and changes from baseline in bone markers will be calculated for each later time point and tested between arms using a t-test or Wilcoxon rank test. If there is sufficient data, a mixed model will be used to model each endpoint over time to determine if the changes are different between treatment arms. Exploratory analysis will use separate Cox models with rPFS, PSA PFS, TTCR, and OS as the individual outcomes and treatment group, one marker, and the interaction between treatment and marker as independent covariates to find associations with outcomes. These models can be expanded to include other subject factors to determine if the marker contributes to outcome above subject factors that are known to be associated with the outcome. Similarly, logistic models can be used with 7-month PSA outcomes. The model analyses are considered exploratory for this trial. Thus, they are not powered and will not use multiple comparisons adjustments.

Worst pain will be reported from the BPI (SF) at each time point with a mean or median and the associated measure of variability and tested between arms with a t-test or Wilcoxon rank test. Comparisons at the times post-baseline will be compared between treatment arms using a paired test (t-test or Wilcoxon rank test.) WHO will be reported categorically by arm at each time point and tested between arms using the Mantel-Haenszel chi-square test. The change in WHO score from baseline will be calculated and be the outcome in a cumulative logistic model. Treatment arm will be included as an independent covariate to test if the change in pain is different between arms. Each post-baseline measure will be a separate model.

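### The WHO analgesic model analyses change from baseline with treatment arm as its only named covariate, giving up precision that adjusting for the baseline score would recover at no cost

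*Combined protocol and SAP*

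**What the plan says.** Secondary objective 2.2.4 covers change in pain level and analgesic use, the latter on the WHO ladder. Two analyses of the WHO score are planned, in the same words in section 12.7 and the synopsis.

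- **Raw score:** "WHO will be reported categorically by arm at each time point and tested between arms using the Mantel-Haenszel chi-square test". No stratification by, or adjustment for, the baseline score is mentioned.
- **Change:** "The change in WHO score from baseline will be calculated and be the outcome in a cumulative logistic model". On covariates: "Treatment arm will be included as an independent covariate to test if the change in pain is different between arms". On time points: "Each post-baseline measure will be a separate model".

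The scale is set out in section 9.5, part B: "a single numeric score (0, 1, 2 or 3) will be assigned based on the scale as above". Baseline is available in both induction groups: "Score will be assigned pre-treatment on Cycle 1 Day 1 of (Late Induction group) or Cycle 2 Day 1 (Early Induction group"). Section 5.4 starts radium-223 on Cycle 2 Day 1, so this score precedes any radium-223 in either group. Section 3.1 admits men who have two or more "skeletal lesions with or without pain at baseline on bone scan or axial imaging", so men who use no analgesic can enter.

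**The concern.** The set of possible changes depends on where a man starts: 0 to +3 from a score of 0, -1 to +2 from 1, -2 to +1 from 2, and -3 to 0 from 3. A change of zero therefore groups men who never need an analgesic with men who stay on strong opioids. A one-step fall from 3 to 2 counts the same as one from 1 to 0.

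Baseline explains much of this spread, but the model as written does not use it. The sentence in 12.7 that lets models be expanded with other subject factors follows the Cox marker models and does not reach the WHO model. Reading arm as the sole covariate is an inference from silence, but it is the plain reading.

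What is at stake is precision on part of one secondary objective, in a trial with few controls: "Randomization of 68 subjects to the ADT arm and 136 subjects to the ADT+R arm will be completed".

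**Working it through.** **The plan's own figures.** None is given for the WHO analysis. The primary-endpoint figure reproduces: (1.2816 + 1.2816)² / [(1/3)(2/3)(ln(12/19))²] = 6.57 / 0.0469 = 140 events. With exponential rPFS, 24 months' accrual, 48 months' duration and 10% yearly dropout, 204 subjects give 140.1 events. This says nothing about the WHO score. It supplies only the arm sizes (68 and 136) and a level to borrow (one-sided 0.10), since section 12 sets no level for this analysis.

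**Benchmark without limits.** For an unbounded score with equal variances and baseline-to-follow-up correlation r, the unadjusted change has variance 2σ²(1 - r) and the baseline-adjusted outcome has σ²(1 - r²). The information kept is (1 - r²) / [2(1 - r)] = (1 + r)/2. That is 0.65 at r = 0.3, 0.75 at r = 0.5 and 0.85 at r = 0.7.

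**With the 0-3 limits.** All inputs except the arm sizes are assumed.

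- Baseline percentages at 0/1/2/3: 70/15/10/5, 50/25/15/10, 30/30/25/15, or 25 each.
- Latent bivariate normal scores with r = 0.3, 0.5 or 0.7, cut to 0-3.
- Common improvement of 0 or 0.3 SD, and a further 0.4 SD on radium-223.

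Proportional-odds models were fitted to the expected cell counts. Their likelihood-ratio noncentralities λ were compared, with power = Φ(√λ - 1.2816).

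Worked setting: 50/25/15/10, r = 0.5, common improvement 0.3 SD.

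| Model | λ | Power | Information relative to last row |
|---|---|---|---|
| Change on arm (the plan) | 2.60 | Φ(1.612 - 1.282) = 0.63 | 0.47 |
| Change on arm and baseline category | 5.07 | Φ(2.252 - 1.282) = 0.83 | 0.91 |
| Post-baseline score on arm | 4.63 | Φ(2.152 - 1.282) = 0.81 | 0.83 |
| Post-baseline score on arm and baseline category | 5.59 | Φ(2.364 - 1.282) = 0.86 | 1 |

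The planned model loses about 53% here, against 25% for an unbounded score at the same r, so both sources contribute. In this setting 39% of control subjects start at 0 and stay there. A 400-run simulation of the same setting gave power 0.62, 0.85, 0.82 and 0.87 in row order.

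**Range over assumptions.**

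- Improvement scenarios (24 settings): the planned model keeps 0.35 to 0.77, a loss of 23% to 65%. In every setting it keeps less than (1 + r)/2.
- Scores mostly worsening, r from 0.2 to 0.85: a loss of 5% to 48%.
- Log odds ratio of -0.75 under assumed baseline mixes and dependence (18 settings): the planned model keeps 44% to 93%. Power at one-sided 0.10 is about 61-89% as planned and 83-92% adjusted.

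**Type I error.** With no treatment effect, 400 runs at nominal 0.10 rejected in 0.105 (planned) and 0.110 (post-baseline score adjusted for baseline). The Monte Carlo standard error is √(0.1 × 0.9/400) = 0.015.

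**The case against.** **The raw score is tested anyway.** This stands in part. The by-visit tables show how many men use no analgesic and how many use strong opioids, and the Mantel-Haenszel test does not depend on the change score. An unadjusted post-baseline model, used as a stand-in for that test, keeps about 61% to 96% of the adjusted information in the improvement scenarios. It falls furthest short at high correlation. At 50/25/15/10, r = 0.7 and no common improvement it keeps 0.63, against 0.68 for the planned change model. A reader might infer that the change model is the only analysis of analgesic use. It is the only regression model for it, not the only test.

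**Proportional odds.** A reader might infer that the floor and ceiling make proportional odds impossible. They do not. The model conditions on arm alone, and randomisation gives both arms the same expected baseline mix, so the assumption concerns two marginal distributions of change. A linear-programming check with a 50/25/15/10 baseline and all limits respected found transition tables that satisfy it exactly at log odds ratios of 0.3, 0.5 and 0.75. Under no effect it holds trivially. The odds ratio is a marginal one for a better change, and pooling starting levels makes it harder to interpret without making it meaningless.

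**The size is assumed.** This stands. The documents give no distribution, correlation or effect. Generating data from the recommended model would also favour that model, which is a reason to give weight to the latent-normal scenarios. Absolute power depends on the borrowed significance level, but the information ratio does not.

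**It is secondary and unpowered.** This also stands, and it limits how much weight the point can carry.

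**Conclusion.** The point holds as a loss of precision. The planned model omits a baseline score that the trial already collects, and it was less efficient than the adjusted model in every scenario examined. The loss runs from roughly 5% to 65% of the treatment-effect information. A narrower range would claim more than the documents allow. The loss should not be put down to the floor and ceiling alone, because any unadjusted change score carries some of it.

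A reader might also infer that the analysis is invalid or that the trial's main conclusion is at risk. Neither follows: the simulation showed no type I error inflation, and rPFS is analysed separately. This is an efficiency improvement to one part of objective 2.2.4.

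**What to change.** In section 12.7 and the matching synopsis text, make the WHO score (0-3) at each post-baseline visit the outcome of the cumulative logistic model. Include treatment arm and baseline WHO score, entered as categories, as covariates. State that sparse baseline levels will be merged if needed, since few of the 68 controls may start at the top of the scale. Keep the change in score as a descriptive table. Adding the two stratification factors (extent of disease and alkaline phosphatase) is optional; their effect was not tested here.

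The cost is a sentence or two in each place. No new data, visits or changes in conduct are needed. The change should be made before any results by arm are seen.

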## 13 TRIAL MANAGEMENT

### 13.1 Data and Safety Monitoring Plan:

The study will be conducted in accord with University of Michigan Comprehensive Cancer Center's Data and Safety Monitoring Plan.

HCRN data and safety monitoring activities include:

- Conduct review of clinical trial for progress and safety
- Review of all adverse events requiring expedited reporting as defined in the protocol
- Provide sponsor-investigator with trial progress and safety information **monthly**.
- Notification of participating sites of adverse events requiring expedited reporting
- Submit data summary reports to the DSMB for review according to DSMB Charter

### 13.2 Data Safety Monitoring Board

This study will have a Data and Safety Monitoring Board (DSMB) that will review and monitor study progress, toxicity, safety and other data from this trial. The DSMB is separate from the Data and Safety Monitoring Committee (DSMC) referred to above. The board is chaired by an independent medical oncologist external to this trial. Questions about subject safety or protocol performance will be addressed with the sponsor-investigator, statistician, and study team members. Should any major concerns arise; the DSMB will offer recommendations regarding whether or not to suspend the trial.

The DSMB will meet quarterly to review accrual, toxicity, response, and reporting information. Information to be provided to the DSMB may include subject accrual, treatment regimen information, adverse events, and serious adverse events reported by category, summary of any deaths on study, audit, and/or monitoring results.

The DSMB will provide a recommendation to the sponsor-investigator and HCRN after all information is reviewed. HCRN will provide this information to participating sites, who will submit it to their IRB at the time of continuing review.

### 13.3 Data Quality Oversight Activities

Remote validation of OnCore data will be completed on a continual basis throughout the life cycle of the study. A summary report (QC Report) of these checks together with any queries resulting from manual review of the eCRFs will be generated for each site and transmitted to the site and the site monitor. Corrections will be made by the study site personnel.

There will be at least one routine visit per site per year for sites that have accrued. Additional for cause visits may occur as necessary. Source documents will be reviewed for verification of agreement with data entered into OnCore. It is important for the site investigator and their relevant personnel to be available for a sufficient amount of time during the monitoring visits or audit, if applicable. The site investigator and institution guarantee access to source documents by HCRN or its designee.

The trial site may also be subject to quality assurance audit by Bayer or its designee as well as inspection by appropriate regulatory agencies.

### **13.4 Compliance with Trial Registration and Results Posting Requirements**

Under the terms of the Food and Drug Administration Modernization Act (FDAMA) and the Food and Drug Administration Amendments Act (FDAAA), the sponsor-investigator of the trial is solely responsible for determining whether the trial and its results are subject to the requirements for submission to the Clinical Trials Data Bank, <http://www.clinicaltrials.gov>. All results of primary and secondary objectives must be posted to CT.gov within a year of completion. The sponsor-investigator has delegated responsibility to HCRN for registering the trial and posting the results on clinicaltrials.gov. Information posted will allow subjects to identify potentially appropriate trials for their disease conditions and pursue participation by calling a central contact number for further information on appropriate trial locations and study site contact information.

## **14 DATA HANDLING AND RECORD KEEPING**

### **14.1 Data Management**

HCRN will serve as the Clinical Research Organization for this trial. Data will be collected through a web based clinical research platform, OnCore, a system compliant with Good Clinical Practices and Federal Rules and Regulations. HCRN personnel will coordinate and manage data for quality control assurance and integrity. All data will be collected and entered into OnCore by study site personnel from participating institutions.

### **14.2 Case Report Forms and Submission**

Generally, clinical data will be electronically captured in OnCore and correlative results will be captured in OnCore or other secure database(s). If procedures on the study calendar are performed for standard of care, at minimum, that data will be captured in the source document. Select standard of care data will also be captured in OnCore, according to study-specific objectives.

The completed dataset is the sole property of the sponsor-investigator's institution and should not be exported to third parties, except for authorized representatives of appropriate Health/Regulatory Authorities, without permission from the sponsor-investigator and HCRN.

### **14.3 Record Retention**

To enable evaluations and/or audits from Health Authorities/HCRN, the site investigator agrees to keep records, including the identity of all subjects (sufficient information to link records; e.g., hospital records), all original signed informed consent forms, copies of all source documents, and detailed records of drug disposition. All source documents are to remain in the subject's file and retained by the site investigator in compliance with the site contract with HCRN. No records will be destroyed until HCRN confirms destruction is permitted.

### **14.4 Confidentiality**

There is a slight risk of loss of confidentiality of subject information. All records identifying the subjects will be kept confidential and, to the extent permitted by the applicable laws and/or regulations, will not be made publicly available. Information collected will be maintained on secure, password protected electronic systems. Paper files that contain personal information will be kept in locked and secure locations only accessible to the study site personnel.

Subjects will be informed in writing that some organizations including the sponsor-investigator and his/her research associates, HCRN, Bayer, IRB, or government agencies, like the FDA, may inspect their medical records to verify the information collected, and that all personal information made available for inspection will be handled in strictest confidence and in accordance with local data protection laws.

If the results of the study are published, the subject's identity will remain confidential.

## **15 ETHICS**

### **15.1 Ethics Review**

The final study protocol, including the final version of the Written Informed Consent Form, must be approved or given a favorable opinion in writing by an IRB. The site investigator must submit written approval to the HCRN office before he or she can enroll any subject into the study.

The sponsor-investigator is responsible for informing the IRB of any amendment to the protocol in accordance with local requirements. In addition, the IRB must approve all advertising used to recruit subjects for the study. The protocol must be re-approved by the IRB annually, as local regulations require.

Progress reports and notifications of serious unexpected adverse drug reactions will be provided to the IRB according to local regulations and guidelines.

The investigator is also responsible for providing the IRB with reports of any serious adverse drug reactions from any other study conducted with the investigational product. Bayer HealthCare Pharmaceuticals will provide this information to the Sponsor Investigator. These reports will be reviewed by the Sponsor Investigator and those considered unexpected and possibly related to protocol therapy plus all deaths within 30 days of discontinuing treatment will be forwarded to participating sites for submission to their Institutional Review Boards per their guidelines. All other events will be held and submitted to the sites for continuing review.

